17.1.3. MULTIPLE IMPUTATION UNDER MAR

Any missing PEC at the planned assessments will be imputed using multiple imputation under MAR. MAR assumes the missing value is independent of unobserved outcomes given observed data (i.e., subjects with missing PEC can be modeled based on subjects with observed PEC values) (Rubin 1987).

The following steps will be implemented:

Step 1:

Regardless of the arbitrary missing data pattern (i.e. monotone or non-monotone), a fully conditional specification (FCS) method with predictive mean matching for continuous variables will be used to impute the missing PEC data. The FCS method allows for separate conditional distributions for each imputed variable. The predictive mean matching approach creates a regression model using parameters sampled from the posterior distribution and then a predicted value for each missing value is computed. The missing value is replaced by randomly selecting an observation from a set of 'k' values that are the closest predicted values to the missing predicted value. Missing data imputation will be performed using the SAS PROC MI procedure. The number of imputations will be 40. A separate imputation model will be used for each treatment group. The stratification variables will be included in the imputation models.

Step 2:

Percent change from Baseline in PEC will be re-computed at Week 16 for each of the 40 imputed datasets.

Step 3:

The analysis of covariance (ANCOVA) model based on rank scores including treatment group, reported randomization stratification factors of Baseline history of esophageal dilation (Yes/No) and concurrent PPI therapy (Yes/No) as factors and Baseline eosinophil PEC as a covariate will be run for each of the 40 datasets to obtain 40 estimators of interest.

Step 4:

Use SAS PROC MIANALYZE to produce an overall pooled estimate (mean of 40 estimates) with its associated standard error, confidence interval, and pooled p-value.

There could be certain adjustments to the multiple imputation model due to unexpected data issues after unblinding

treatment. All post-unblinding modifications to the multiple imputation model or approaches to address missing data will be described in the Clinical Study Report (CSR).

Additionally, missing data will be imputed using the following missing data methods: Tipping point analysis and observed data only. More details are provided in Section 16.1.5.

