Study Design: 
This Phase 2, randomized, double-blind, multi-center study will evaluate the efficacy, safety, and pharmacokinetics (PK) of etrasimod compared with placebo in adults with active EoE. The study will consist of a Screening Period of up to 35 days, 24 weeks of double-blind treatment (Double-Blind Treatment Period), 28 weeks of active extended treatment (Extension Treatment Period), and 4 weeks of follow-up (Safety Follow-Up Period) for a total study duration of up to 61 weeks.
 
Eligible subjects will be randomized in a double-blind fashion (3:3:2 ratio) to etrasimod 1 mg, etrasimod 2 mg, or matching placebo once daily. Randomization will be stratified by baseline history of esophageal dilation (yes/no) and concurrent proton pump inhibitor (PPI) therapy (yes/no).
 
All subjects who complete the Double-Blind Treatment Period and meet eligibility criteria for the Extension Treatment Period may enter the Extension Treatment Period. Subjects who were in the etrasimod 1 mg or etrasimod 2 mg groups in the Double-Blind Treatment Period will continue the same etrasimod dose in the Extension Treatment Period. Subjects who were in the placebo group during the Double-Blind Treatment Period will be re-randomized (1:1 ratio) to etrasimod 1 mg or etrasimod 2 mg at entry into the Extension Treatment Period.
 
Subjects will have follow-up visits at 2 and 4 weeks after the last dose of study treatment after Week 52 or the Early Termination (ET) Visit.

Number of Subjects (planned):

Approximately 96 subjects are planned to be enrolled.

Eligibility Criteria for the Double-Blind Treatment Period:

Key Inclusion Criteria (Full Inclusion Criteria Are Provided in the Protocol)

- Men or women between 18 and 65 years of age at the time of informed consent (IC)
- Have an EoE diagnosis prior to screening and histologically active disease with an esophageal peak eosinophil count (PEC) of ≥ 15 eosinophils (eos)/high power field (hpf) (~ 60 eos/mm²) from any level (proximal, mid, or distal) of the esophagus at the Screening esophagogastroduodenoscopy (EGD)
- Have dysphagia, defined as solid food going down slowly or getting stuck in the throat with an average frequency of ≥ 2 episodes per week over 2 weeks (as documented using the Dysphagia Symptom Questionnaire (DSQ) during the Screening period)

Key Exclusion Criteria (Full Exclusion Criteria Are Provided in the Protocol)

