11.5. Efficacy Analyses

For the Double-Blind Treatment Period, the primary and secondary endpoints will be analyzed using the FAS. Other important statistical considerations, such as handling rescue medication/rescue procedure uses during study treatment, missing data imputation strategies, sensitivity analyses, and subgroup analyses will be described in the SAP.

The endpoints of percentage change in esophageal PEC from Baseline to Week 16 and Week 24 will be analyzed using analysis of covariance (ANCOVA) model based on rank scores due to the skewed distribution of the data and possible outliers. The ANCOVA model will include treatment group and randomization stratification factors as factors and Baseline eosinophil PEC as a covariate. PEC after rescue medication/rescue procedure uses will be set to missing; all missing data will be imputed in the FAS using MI procedure as appropriate. Multiple results of ANCOVA (least square [LS] mean rank scores and LS mean rank score difference from placebo) for each MI dataset will be analyzed and reported along with final p-value using Rubin's method [1]. In addition, a descriptive summary of percentage change in esophageal PEC from baseline as well as the difference between treatment groups will be presented by treatment group. When applying the same ANCOVA model to key secondary continuous variables, norank transformation will be used.

For the efficacy endpoints of the percentage change in esophageal PEC from Baseline at Week 16 and Week 24, in the FAS, subjects who have experienced intercurrent events, such as rescue medication/rescue procedure use, early discontinuation of study treatment, etc., will be included in the analysis and their missing data at Week 16 and Week 24 will be imputed using a MI model. The MI model will take into consideration the reason and nature of intercurrent event leading to missing data. A detailed plan for constructing and analyzing the primary estimand will be described in the SAP.

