3. STUDY DESIGN

3.1. GENERAL DESCRIPTION

[figure not shown]
This Phase 2 randomized, double-blind, multi-center study will evaluate the efficacy, safety, and PK of etrasimod compared with placebo for 24 weeks in adults with active EoE.

The study will consist of a Screening Period of up to 35 days, 24 weeks of double-blind treatment (Double-Blind Treatment Period), 28 weeks of active extended treatment (Extension Treatment Period), and 4 weeks of follow-up (Safety Follow-Up Period) for a total study duration of up to 61 weeks. Approximately 96 subjects were planned to be enrolled.

Eligible subjects will be randomized in a double-blinded fashion (3:3:2 ratio) to etrasimod 1 mg, etrasimod 2 mg, or matching placebo once daily. Randomization will be stratified by baseline history of esophageal dilation (yes/no) and concurrent proton pump inhibitor (PPI) therapy (yes/no).

All subjects who complete the Double-Blind Treatment Period and meet eligibility criteria for the Extension Treatment Period may enter the Extension Treatment Period. Subjects who were in the etrasimod 1 mg or etrasimod 2 mg groups in the Double-Blind Treatment Period will continue the same etrasimod dose in the Extension Treatment Period. Subjects who were in the placebo group during the Double-Blind Treatment Period will be re-randomized (1:1 ratio) to etrasimod 1 mg or etrasimod 2 mg at entry into the Extension Treatment Period.

Subjects will have follow-up visits at 2 and 4 weeks after the last dose of study treatment after Week 52 or the Early Termination (ET) visit.

Figure 1: Study Design

*Esophagogastroduodenoscopy

EoE, eosinophilic esophagitis; ETR, etrasimod; F/U, follow-up; PBO, placebo.

Numbers preceded by colons represent the randomization ratio.

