8.4. MULTIPLE COMPARISONS/ MULTIPLICITY

For Double Blinded Treatment Period, hypotheses tests will be performed for efficacy endpoints for the comparison of etrasimod dose versus the placebo group. However, these hypothesis tests will not be controlled for type-I error rate. Un-adjusted p-values will be reported. The associated 95% confidence intervals will be reported.

For the Extension Treatment Period, no hypothesis tests between treatment groups will be performed; only descriptive statistics will be provided.

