17. EFFICACY OUTCOMES

17.1. PRIMARY EFFICACY

17.1.1. PRIMARY EFFICACY VARIABLE & DERIVATION

The primary efficacy variable is percent change from Baseline in esophageal PEC at Week 16. Esophageal PEC will be based on the central esophagogastroduodenoscopy (EGD) results. A decrease in esophageal PEC indicates improvement in disease.

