17.1.4. PRIMARY ANALYSIS OF PRIMARY EFFICACY VARIABLE(S)

The following hypotheses (H01 and H02) for the primary endpoint will be tested:

H₀₁: The percentage change from Baseline in esophageal PEC at Week 16 is the same between etrasimod 2mg and placebo.

H₁₁: The percentage change from Baseline in esophageal PEC at Week 16 is different between etrasimod 2mg and placebo.

H₀₂: The percentage change from Baseline in esophageal PEC at Week 16 is the same between etrasimod 1mg and placebo.

H₁₂: The percentage change from Baseline in esophageal PEC at Week 16 is different between etrasimod 1mg and placebo.

All hypotheses will be tested at the 2 sided α level, 0.05.

The primary efficacy analysis will be performed for the FAS. Percent change from baseline in esophageal PEC will be summarized using the number of observations, mean, standard deviation (SD), median, minimum, and maximum. An analysis of covariance (ANCOVA) model based on rank scores due to the skewed distribution of the data and possible outliers will be used. The ANCOVA model will include treatment group and randomization stratification factors of Baseline history of esophageal dilation (Yes/No) and concurrent PPI therapy (Yes/No) as factors and Baseline eosinophil PEC as a covariate. Multiple results of the ANCOVA model will be expressed as least square (LS) means rank scores, LS mean rank scores difference from placebo, 95% confidence interval (CI) and p-value. For the treatment comparisons of etrasimod 1 mg vs. placebo and etrasimod 2 mg vs placebo, the treatment group factor in the ANCOVA model will include placebo, etrasimod 1 mg and etrasimod 2 mg. For the comparison of etrasimod any dose vs placebo, a separate ANCOVA model based on rank scores will be used, where treatment group factor will only include placebo and etrasimod any dose treatment. For the Extension Treatment Period, no pair-wise comparison will be performed; only descriptive statistics will be provided. In addition, descriptive summary of percentage change in esophageal PEC from baseline as well as difference between treatment groups will be presented by treatment group.

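### The primary rank ANCOVA ranks the outcome but names baseline PEC with no transformation; ranking the covariate too costs nothing and could add from zero to several points of power

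*SAP*

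**What the plan says.** SAP 17.1.1 defines the endpoint: "The primary efficacy variable is percent change from Baseline in esophageal PEC at Week 16". SAP 17.1.4 gives the model and the reason for ranks: "An analysis of covariance (ANCOVA) model based on rank scores due to the skewed distribution of the data and possible outliers will be used". Protocol 11.5 lists the terms: "The ANCOVA model will include treatment group and randomization stratification factors as factors and Baseline eosinophil PEC as a covariate". SAP 17.1.3 Step 3 repeats them for the imputed data, with treatment and the two strata "as factors and Baseline eosinophil PEC as a covariate will be run for each of the 40 datasets".

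None of these places says whether baseline PEC is raw, logged or ranked. SAP 17.2.3.1 describes the baseline covariate in the same words for absolute change in PEC, and protocol 11.5 says the key secondary continuous variables are not ranked. The same wording in an unranked model favours reading the covariate as the raw count.

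The table of planned analyses by endpoint in SAP 17.2.1 adds a conflict. Footnote a, on the column headed ANCOVA, says that ranks are not used, and the primary endpoint is marked in that column.

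**The concern.** Skew and outliers are the stated grounds for ranking percent change. Baseline PEC is the same kind of count. It has an entry floor of 15 eos/hpf and no upper limit, and it is the denominator of the endpoint (SAP 6.6), so noise in baseline feeds straight into percent change. If baseline is right-skewed, the rank of percent change falls with baseline along a flattening curve. A straight line in raw counts follows such a curve poorly and is pulled by a few very high baselines.

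What is at stake is precision. Placebo has about 24 subjects, each dose is compared with it separately, and one primary objective is dose selection. The same covariate carries into the pooled-dose, Week 24, tipping-point and supplementary models.

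**Working it through.** **Inputs from the documents**
- Size: "Approximately 96 subjects are planned to be enrolled" (protocol synopsis).
- Allocation: "Eligible subjects will be randomized in a double-blinded fashion (3:3:2 ratio) to etrasimod 1 mg, etrasimod 2 mg, or matching placebo once daily" (SAP 3.1). So 96 × 3/8 = 36 per dose and 96 × 2/8 = 24 on placebo.
- Level: "All hypotheses will be tested at the 2 sided α level, 0.05" (SAP 17.1.4). On multiplicity: "However, these hypothesis tests will not be controlled for type-I error rate" (SAP 8.4).
- Baseline PEC: at least 15 eos/hpf (protocol 4.1 and 10.4.1.1). No median, SD or skewness is given.
- There is no planned power to reproduce, because the sample-size text is redacted. For orientation, with n = 24 and 36, power ≈ Φ(d × √(24 × 36/60) − 1.96) = Φ(3.795d − 1.96). That is 62% at d = 0.6 and 81% at d = 0.75.

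**Why the scale can matter.** Let B be baseline and W be Week 16 PEC. Percent change is 100 × (W/B − 1), so its ranks are the ranks of W/B. Suppose log W = a + β log B + error. Then log(W/B) = a + (β − 1) log B + error, which is linear in log B and not in B.
- If β = 1, percent change is unrelated to baseline and the covariate's scale is irrelevant.
- As β falls towards 0, dependence on baseline grows. With a skewed B, the raw-count line then fits worse.

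**Simulation.** The SAP model was fitted to arms of 24/36/36: rank of percent change on three-level treatment, two binary strata and baseline PEC. Raw and ranked baseline were compared on the same simulated trials, testing 2 mg against placebo. There were 3,000 trials per power setting and 1,500 to 3,000 per null setting.

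Assumptions not in the documents: lognormal baseline with median 60, cut at 15; log-SD 0.5, 0.7 or 0.9 (mean sample skewness about 1.5, 2.2 and 2.9); 0 to 10% missing; no imputation step; no true stratum effects.

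Results at log-SD 0.9 (gains computed before rounding):

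| β (log W on log B) | Residual log-SD | Raw | Ranked | Gain, points |
|---|---|---|---|---|
| 1.0 | 0.8 | 0.730 | 0.735 | 0.4 |
| 1.0 | 1.2 | 0.723 | 0.720 | −0.2 |
| 0.7 | 0.8 | 0.704 | 0.713 | 1.0 |
| 0.7 | 1.2 | 0.733 | 0.737 | 0.4 |
| 0.4 | 0.8 | 0.671 | 0.701 | 2.9 |
| 0.4 | 1.2 | 0.700 | 0.718 | 1.8 |
| 0 | 0.8 | 0.607 | 0.707 | 10.0 |
| 0 | 1.2 | 0.668 | 0.709 | 4.1 |

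At log-SD 0.7 and β = 0, power went from 0.656 to 0.701 and from 0.698 to 0.712. At log-SD 0.5 the gain was −0.1 to +1.1 points.

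Other data patterns gave −0.1 to +2.1 points: Week 16 correlated 0.5 with baseline on the log scale, a responder mixture, or Week 16 linear in raw baseline. Examples at log-SD 0.9 are 0.887 to 0.904, 0.735 to 0.749 and 0.472 to 0.493. Where percent change was proportional by construction the gain was −0.3 to +0.3. Simulation error on these differences was about 0.1 to 0.5 points.

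A separate grid at log-SD 0.8 and baseline-to-Week 16 correlation 0.2 gave 57.5% to 59.8%. With 3% five-fold outliers it gave 57.0% to 61.0%.

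Logged baseline performed like ranked baseline. In the log-SD 0.9, β = 0, residual 0.8 setting it gave 0.717. Type I error was 4 to 6% for the raw and the ranked version.

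**In subjects.** The sample-size ratio is ((1.96 + z_new)/(1.96 + z_old))².
- 0.671 to 0.701: (2.487/2.403)² ≈ 1.07, or about 7% more subjects.
- 0.704 to 0.713: (2.522/2.496)² ≈ 1.02, or about 2%.

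**The case against.** The best case for leaving the plan alone is that it contains no error. A ranked response with a named baseline covariate is a valid prespecified test, and both versions hold the type I error. This is a Phase 2 trial with unadjusted p-values, and dose selection weighs safety as well as efficacy, so a gain that is often under 2 points would rarely change the decision. All of that stands. It limits the size of the point but shows no downside to the change.

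Stronger readings are tempting, and the documents do not support them:
- **The plan loses a fixed amount of power, such as 1 to 7 points.** The documents give no baseline distribution, no baseline-to-Week 16 correlation and no visible power. Every figure above rests on assumed inputs.
- **Baseline PEC is as skewed as the outcome.** The stated reason for ranks refers to the data in general. Baseline is not singled out.
- **The SAP prescribes the raw count.** That is the natural reading but not explicit text. An ANCOVA based on rank scores does not exclude a ranked covariate.
- **Ranking always gains.** With mild skew, or with percent change unrelated to baseline, the difference was zero within simulation error and sometimes slightly negative.

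In reply, complete independence of percent change and baseline is not the likeliest case here. The Screening EGD serves both as the entry test (at least 15 eos/hpf) and as Baseline, and protocol 3.2 itself lists regression to the mean among the expected background effects.

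**Conclusion.** The point holds as a free improvement in efficiency and clarity. The primary test is valid as written. The covariate's scale is unstated and reads as raw. Ranking or logging it was never materially worse in simulation and kept type I error at about 5%.

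The size depends on two things the documents do not show: the skew of baseline PEC and its relation to Week 16 PEC. The power gain is about zero with mild skew or no dependence, typically 0.5 to 5 points with moderate skew and dependence, and larger (up to about 10 points in the most extreme setting) only when Week 16 PEC is nearly unrelated to baseline. The imputation step and true stratum effects were left out. They are not expected to change the direction, but that was not tested.

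The footnote conflict is separate and needs no assumption. One place in the SAP denies ranking for a column that includes the primary endpoint, while 17.1.3 and 17.1.4 require it.

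**What to change.** Before unblinding, in SAP 17.1.3 Step 3, SAP 17.1.4 and protocol 11.5, replace the baseline covariate of the rank ANCOVA with: *the rank of Baseline eosinophil PEC (ranked across the FAS subjects in the model)*. Use the same covariate in the pooled-dose, Week 24, tipping-point and supplementary rank ANCOVAs. Log baseline PEC would serve equally well. What matters is that one scale is named in advance, so that it cannot be chosen after the results are seen.

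In the same edit, restrict or remove footnote a of the planned-analyses table in SAP 17.2.1 so that it agrees with 17.1.3 and 17.1.4. Protocol 11.5 drops ranks only for the key secondary continuous variables.

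The cost is one phrase and one derived variable. It needs no new data and has no type I error cost.

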11. PLANNED STATISTICAL METHODS

11.1. General Considerations

Details regarding the statistical analyses will be provided in the Statistical Analysis Plan (SAP), which will be finalized prior to database lock and unblinding.

Continuous variables will be summarized using the number of observations, mean, standard deviation (SD), median, minimum, and maximum. Categorical variables will be summarized using frequency counts and percentages.

For Double Blinded Treatment Period, hypotheses tests will be performed for efficacy endpoints for the comparison of etrasimod dose versus the placebo group. However, these hypotheses tests will not be controlled for type-I error rate. Un-adjusted p-values will be reported.

For the Extension Treatment Period, no hypothesis tests between treatment groups will be performed; only descriptive statistics will be provided.

The SAP will describe an overall plan to address the alignment between the target of efficacy estimation (ie, trial objective, or estimand of interest), the analysis set, the method of estimation, and primary method to handle intercurrent events; along with a plan of sensitivity analysis to evaluate the robustness of findings that can sustain limitations in missing data and intercurrent events of non-adherence to protocol.

Efficacy data will be analyzed by randomized treatment, while safety data will be analyzed by actual treatment.

CCI [REDACTED]

[REDACTED]

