5.1. PROCESS FOR ANALYSIS SET ASSIGNMENT

Before the database is unblinding for the Main Analysis and Final Analysis, the subjects excluded from each analysis set and the reason for exclusion will be sent to Pfizer for blinded review. The Clinical Protocol Deviation log file will be needed to define the Per Protocol Set for each analysis. This file will be incorporated into the analysis datasets and used, along with programmable deviations, to determine which subjects to include in the Per Protocol Set. Any changes to the analysis sets will occur before the database is unblinded. Pfizer will approve the final analysis sets which will be used for analyses prior to database unblinding. Once the analysis sets are approved, the subjects will be unblinded. Any additional analysis set assignments after database unblinding will also need to be approved.

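### The imputation model behind the primary analysis may be changed after unblinding, and description in the CSR is the only stated safeguard

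*SAP*

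**What the plan says.** SAP 17.1.3 specifies the primary imputation: fully conditional specification with predictive mean matching, 40 imputations, a separate model for each arm, and the stratification variables in each model. ANCOVA on ranks and Rubin pooling follow. The section then adds: "There could be certain adjustments to the multiple imputation model due to unexpected data issues after unblinding". The sentence after it widens the scope and gives the only condition: "All post-unblinding modifications to the multiple imputation model or approaches to address missing data will be described in the Clinical Study Report (CSR").

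The model feeds the tests of each dose against placebo in SAP 17.1.4: "All hypotheses will be tested at the 2 sided α level, 0.05". SAP 8.4 says of the efficacy tests that "these hypothesis tests will not be controlled for type-I error rate".

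On analysis sets, SAP 5.1 states that changes are made before unblinding, but it ends: "Any additional analysis set assignments after database unblinding will also need to be approved". Protocol 11.1 describes the SAP as a document "which will be finalized prior to database lock and unblinding".

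**The concern.** A model choice made with the arms visible can be influenced by the result, even if nobody intends it. Describing the change in the CSR tells the reader that the model moved. It does not restore the 5% level, and it does not tell the reader what the unmodified model would have shown, because the SAP does not require that result to be reported.

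Both primary comparisons use this model. Choosing a dose for further development is a primary objective (SAP 2.1), and SAP 2.4 presents the estimands as supporting regulatory decisions.

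**Working it through.** **1. What is locked before unblinding.**

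- Rescue use, which decides which PEC values become missing: finalized before unblinding (SAP 17.1.2 and Appendix 4).
- Per Protocol exclusion flags: finalized before unblinding (SAP 5.5).
- Set membership: agreed before unblinding (SAP 5 and 5.1, apart from the last sentence of 5.1).
- FAS, the primary population: fixed by rule as randomized and dosed at least once (SAP 5.4).
- Imputation model: may change after unblinding (SAP 17.1.3).

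The imputation model is the exception.

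**2. How much of the model is open.** SAP 17.1.3 names the number of matching donors, k, without giving it a value. It gives no seed, no complete predictor list and no fallback. Protocol 11.4.1 says that rescue use, reasons for discontinuation and time on treatment will inform the imputation and leaves the detail to the SAP. Besides treatment arm, SAP 17.1.3 names only the stratification variables.

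**3. Size, by illustration.** The plan has no figure to reproduce. The documents show no missing-data rate, and the sample-size text is blacked out.

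Inputs from the documents: "Approximately 96 subjects were planned to be enrolled" and "Eligible subjects will be randomized in a double-blinded fashion (3:3:2 ratio) to etrasimod 1 mg, etrasimod 2 mg, or matching placebo once daily". This gives 96 × 3/8 = 36, 96 × 3/8 = 36 and 96 × 2/8 = 24 (placebo). The level is two-sided 0.05, with 40 imputations.

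Assumptions, not in the documents:
- lognormal PEC with no treatment effect;
- Week 16 values missing completely at random at 5%, 10%, 20% or 30%;
- dilation history 30% and PPI use 40%;
- k = 5 in the reference model;
- only Week 16 imputed, from baseline and strata;
- baseline PEC ranked in the ANCOVA.

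There were 1,500 simulated trials per setting.

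Pooling: T = Ū + (1 + 1/40)B and t = q̄/√T, where q̄ is the mean of the 40 estimates, Ū the mean within-imputation variance and B the between-imputation variance.

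The eight variants were by-arm matching with k = 1, 5 (the reference) and 10; by-arm matching without strata; one model across arms, with and without an arm term; by-arm lognormal regression; and observed data only.

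Type I error, 2 mg against placebo:

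| Missing Week 16 PEC | One fixed model | Smallest p of eight | Increase (points) | Median p-value spread across variants |
|---|---|---|---|---|
| 5% | 5.1% | 6.5% | 1.4 | 0.11 |
| 10% | 6.1% | 7.6% | 1.5 | 0.16 |
| 20% | 6.5% | 9.1% | 2.6 | 0.24 |
| 30% | 6.9% | 12.4% | 5.5 | 0.31 |

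The fixed model is one of the eight, so the increase d is the share of trials in which it is not significant but another variant is. The Monte Carlo standard error is √(d(1 − d)/1500): 0.3 points at d = 0.014 and 0.6 points at d = 0.055. The increase must be read against the fixed model, not against 5%, because the fixed model itself runs somewhat above 5% here.

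Varying only k and the strata terms within by-arm matching gives 6.3%, 7.5%, 8.9% and 12.1%. Nearly all of the room to move therefore comes from modest tuning.

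**4. Cross-check.** Take the best of several test statistics with an assumed common correlation, and compute P(any |z| > 1.96). At correlation 0.95, two, three and five variants give 6.4%, 7.3% and 8.5%. Two variants at 0.98 give about 6%, and five at 0.90 give 10.2%. The direction is the same, and the size again depends on the assumption.

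**The case against.** Much of the case on the other side stands, and it rules out four stronger readings.

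- **That analysis-set changes also reach the primary p-value.** A reader might infer this from the last sentence of SAP 5.1. The primary analysis uses the FAS, which is set by rule, and SAP 5, 5.1 and 5.5 place set decisions before unblinding. The sentence is an internal inconsistency that could touch supplementary sets. It may be meant for Extension Period sets, since sponsor staff are unblinded at the Main Analysis (SAP 4.1), but it does not say so.
- **That the SAP authorizes picking the result.** It does not. Changes are tied to unexpected data issues and must be disclosed. The SAP fails to prevent selection, which is a weaker statement.
- **That the clause breaches Protocol 11.1.** A SAP can be final before unblinding and still contain a contingency clause, and SAP 4.1 bars unblinding until the SAP is approved.
- **That the clause is likely to be used because placebo has about 24 subjects.** The documents give no missing-data rate or stratum prevalence. Randomization is stratified by the same two factors, and a baseline value plus two binary factors does not make a failed fit probable.

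Two further points temper the severity. This is a Phase 2 trial that reports unadjusted p-values. The planned observed-data analysis (SAP 17.1.6.2) also gives a benchmark free of imputation against which an altered model would show. The tipping point analysis helps less, because it reuses the same imputation step.

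The gap in SAP 17.1.3 remains: an undefined trigger, a scope wider than the model itself, and no rule that the specified result stays primary.

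**Conclusion.** The concern holds for the imputation model and the wider missing-data approach, and only there. SAP 17.1.3 leaves the primary Week 16 PEC p-values open to decisions made after the arms are known. If the best of several variants were kept, the illustration puts the rise in type I error at about 1.4 points with 5% missing Week 16 PEC and about 5.5 points with 30%. It is small when few biopsies are missing and material when many are. These figures rest on the assumed distribution, missingness mechanism and set of variants. They show what the clause leaves possible and do not predict what the sponsor would do.

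The inconsistency in SAP 5.1 is a separate, smaller matter that leaves the primary FAS analysis untouched. Given the phase and the absence of type I error control, this is a cheap improvement that should be made before unblinding, and not a condition for the trial to be interpretable.

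**What to change.** 1. Delete the post-unblinding clause from SAP 17.1.3.
2. Before unblinding, state k, the full predictor list and the seed.
3. Write an ordered fallback, triggered only if the specified model fails to fit. A dry run with dummy arm codes would test the program but cannot reveal sparsity in the real arms, so the fallback has to be written out in advance.
4. State that the pre-specified model, or its pre-written fallback, gives the primary result, and that any later variant is reported beside it as post hoc.
5. Reconcile the last sentence of SAP 5.1 with that section's own rule that set changes come before unblinding, for example by limiting it to Extension Period sets.

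The cost is SAP wording and less freedom to adapt the model after unblinding. Item 4 alone closes most of the gap.
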